In Phase II, we will conduct an evaluation of the intervention applying a group-randomized design with village as the unit of assignment. Sixteen villages were selected and randomly assigned to receive the intervention (8 villages) or control condition (8 villages) with ≥ 22 pregnant women recruited per village.

Subject population:

Sample size calculation. We estimate recruiting ≥ 22 pregnant women per village (N=352). Accounting for an estimated attrition rate of 10% due to miscarriage, abortion or fetal demise, we plan to achieve a final sample of at least 320 women eligible for follow-up. All pregnant women (tobacco users and non-users) will be eligible for enrollment.

Actual accrual. We met our targeted sample size of 352 women enrolled. Encouragingly, overall participation from control villages (n=164) was similar to overall participation from intervention villages (n=188). Although we estimated 22 or more women enrolled in each village, this was not feasible. Study villages were more or less interested in participating, with a range of 2 to 42 women enrolled in the 16 study villages.

Inclusion Criteria:

Participants consist of 352 Alaska Native pregnant adults age 18 and older. To be eligible for the study, Alaska Native pregnant women participants must:

- Be 18 years of age or older
- Provide written informed consent
- Currently 36 weeks or less gestation
- Access to a working telephone

Exclusion Criteria:

Individuals will be considered ineligible to participate in the study if they are:

- Not Alaska Native
- Under the age of 18
- Currently not pregnant or ≥ 37 weeks gestation
- No access to a working telephone
- Refuse to provide written informed consent

Will a Certificate of Confidentiality be obtained? If yes, provide an explanation.

No, a Certificate of Confidentiality will not be obtained.

Study Design

Methods: *Describe, in detail, the research activities that will be conducted under this protocol:*

Phase IA. Social Marketing Campaign Development

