who quit tobacco use during pregnancy, the relapse rate was 63% at 6 weeks postpartum. Of the 432 women reporting no tobacco use in the three months before pregnancy, 75% reported tobacco use during the prenatal period, and 70% at 6 weeks postpartum. Alaska PRAMS data indicate similar cessation rates during pregnancy (20%) and rates of relapse postpartum (57%) in the southwest region. During the time periods these estimates were obtained, women received the same standard of care as in the proposed study. Therefore, we do not expect our usual care condition to impact tobacco use beyond the natural history of tobacco use in pregnancy. The Clinical Practice Guideline meta-analysis found that behavioral/psychosocial interventions for pregnant smokers were associated with an abstinence rate of 13% in late pregnancy vs. 7% for control conditions (OR= 1.8, 95% CI 1.5-2.3). We do not have guidance from the literature on the possible impact of interventions for baseline non-tobacco users but would expect greater impact in this group compared to those already using tobacco. Accordingly, we estimate the rate of tobacco use at 6 months postpartum to be 70% in our control villages and 55% in the intervention villages (estimated odds ratio 1.91) and in late pregnancy to be 80% vs. 65% with an odds ratio of 2.15. A difference of 15% would be of clinical significance in terms of the potential to impact the current standard of care at the YKDRH.

Estimates of intra-class correlations (ICC) within communities are quite modest, e.g., ranging from 0.002 to 0.012 for a variety of survey variables included in the Minnesota Heart Health Program. For the proportion currently smoking the estimated ICC was 0.00272. Other literature indicates that in community based trials using group-randomized designs (e.g., NCI Working Well Trial) the ICC ranged from 0.01-0.03 for the four outcome variables at baseline. Lumley et al. reviewed 9 cluster randomized trials of prenatal cessation interventions but most did not report the ICC and/or account for the clustering effect in the analysis. Table 3 (below) provides power estimates for the estimated outcomes with 16 villages total, average village participant size of 20 (total sample size = 320), and with varying ICC estimates. With an ICC of 0.01 we will have >80% power to detect the hypothesized differences between conditions at 6 months postpartum.

Table 3. Power estimates for 1-sided alpha=0.05 test

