ICC	Hypothesized difference in tobacco use rates	
	Late Pregnancy 65 vs. 80%	6 Months Postpartum 55 vs. 70%
0	91	87
0.001	91	86
.01	86	81
.02	82	76
.03	77	71

Data Analysis Plan:

Analyses will be performed by [name], M.S. who has extensive experience in analysis of randomized clinical

trials, with consultation from [name]. Recruitment data will be summarized, including the total number of potential participants screened from each village, the number excluded for each of the specific inclusion/exclusion criteria, and the number of eligible women who agree to participate. To assess reach of the program in each village, we will calculate the proportion of subjects enrolled to total eligible subjects. We will compare the recruitment rates between control and intervention villages using the chi-square test. Potential village effects on recruitment rate will be explored.

Baseline demographics will be summarized and compared between intervention and control villages using the chi-square test for categorical variables and the two-sample t-test/rank sum test for continuous variables. The biochemically confirmed 7-day point prevalence tobacco use rate at 6 months postpartum will be summarized for each condition (point estimate and 95% CI) among participants eligible for follow-up (i.e., excluding women experiencing a miscarriage, abortion or fetal demise) and compared between conditions using generalized estimating equations (GEE) with a logit link function to account for clustering of outcomes within village (ICC) (**Aim 1**). We will utilize an intent-to-treat approach, with participants eligible but lost to follow-

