up or who do not provide biochemical confirmation classified as using tobacco. The analysis will be supplemented with multiple imputation methods to classify lost to follow-up as tobacco users or non-users. GEE will also be used to examine condition differences on the point prevalence tobacco use rates at 12 weeks/week 36 gestation, and at 8 weeks postpartum. Because only 14 df are available for the test of the intervention we will employ a small sample correction to the standard GEE. For these analyses, the stratification factor (village size) will be adjusted for in the analysis. Based on the biochemically confirmed tobacco use status at baseline, in an exploratory fashion we will examine potential treatment effects separately among baseline non-tobacco users and tobacco users respectively using GEE. Within intervention villages only, exposure dose will be tested as a predictor of tobacco use at 36 weeks gestation and 6 months postpartum using GEE. A similar analysis will be performed using the intervention implementation index to examine potential dose response effects. Assuming an ICC of 0.01 and an effective sample size of 135 subjects in the intervention arm after correction for the ICC, there will be 80% power to detect an effect size of at least 0.5 standard deviation units when examining the association of intervention exposure (i.e., continuous measure) and abstinence rates. Potential village differences on intervention exposure or implementation will be summarized graphically and compared using GEE. The percentage of enrolled participants who complete 6- month follow-up postpartum (retention) will be compared between intervention and control villages using GEE.

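### The stated >80% power at 6 months postpartum leaves out the plan's own 14 degrees of freedom; with them it is about 78–79%, and lower with the village sizes actually enrolled

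*Combined protocol and SAP*

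**What the plan says.** The Power Statement (Statistical Considerations, Phase II) assumes tobacco use at 6 months postpartum of 70% in control villages and 55% in intervention villages. It uses 16 villages, with "average village participant size of 20 (total sample size = 320), and with varying ICC estimates". The table is headed "Table 3. Power estimates for 1-sided alpha=0.05 test" and prints 87, 86, 81, 76 and 71% for 6 months postpartum at ICCs of 0, 0.001, 0.01, 0.02 and 0.03. The text concludes: "With an ICC of 0.01 we will have >80% power to detect the hypothesized differences between conditions at 6 months postpartum".

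The Phase II Data Analysis Plan specifies a logit-link GEE that accounts for clustering by village. It then says: "Because only 14 df are available for the test of the intervention we will employ a small sample correction to the standard GEE". It adds: "For these analyses, the stratification factor (village size) will be adjusted for in the analysis". The Actual accrual paragraph reports 352 women enrolled, 188 in intervention and 164 in control villages, "with a range of 2 to 42 women enrolled in the 16 study villages".

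**The concern.** The power calculation and the analysis plan do not appear to describe the same test. A comparison of 8 villages with 8 villages has 14 df, as the plan recognises, and the heavier tails of the t distribution cost power. The Power Statement mentions neither the degrees of freedom nor variation in village size, and its 81% leaves only one point of margin over 80%. If the calculation used a normal reference and equal villages, the stated threshold could be missed on the plan's own inputs. A null result would then be read against a power figure that the planned test does not have.

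**Working it through.** **Inputs.** Rates 0.55 and 0.70, ICC 0.01, 16 villages averaging 20 women, N = 320 (Power Statement); one-sided alpha 0.05 (Table 3 heading); 8 villages per arm (Randomization); 14 df (Data Analysis Plan).

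**Effective sample size.** Design effect = 1 + (20 − 1) × 0.01 = 1.19. Per arm, 160/1.19 = 134.45; in total, 268.9. The Data Analysis Plan's own effective sizes of 135 (one arm) and 270 (both arms) agree, which supports the reading that equal villages of 20 were assumed.

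**Standardised effect δ, three usual forms.**
- Risk difference, unpooled: 0.15/√[(0.55×0.45 + 0.70×0.30)/134.45] = 0.15/0.0583 = 2.571
- Risk difference, pooled: 0.15/√[2×0.625×0.375/134.45] = 0.15/0.0590 = 2.540
- Log-odds (the scale of the planned GEE): [ln(0.70/0.30) − ln(0.55/0.45)]/√[1/(134.45×0.2475) + 1/(134.45×0.21)] = 0.6466/0.2559 = 2.527

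**Reproducing the plan.** Normal power = Φ(δ − 1.645): 82.3%, 81.5% and 81.1%, against 81% printed. The log-odds form matches all five printed 6-month cells after rounding.

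**With 14 df.** Power = P(T > 1.761), where T is noncentral t with 14 df and noncentrality δ: 78.8%, 77.9% and 77.6%. With 13 df (critical value 1.771): 78.5%, 77.6% and 77.3%.

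| ICC | Table 3 | Normal, log-odds | 14 df, log-odds | 14 df, unpooled |
|---|---|---|---|---|
| 0 | 87 | 86.7 | 83.5 | 84.6 |
| 0.001 | 86 | 86.1 | 82.9 | 84.0 |
| 0.01 | 81 | 81.1 | 77.6 | 78.8 |
| 0.02 | 76 | 75.9 | 72.1 | 73.4 |
| 0.03 | 71 | 71.1 | 67.3 | 68.6 |

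The 14-df figures are 2 to 4 points below every printed cell, so Table 3 did not use 14 df.

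**Unequal villages.** Design effect = 1 + [(1 + CV²) × 20 − 1] × 0.01. The documents give only the mean (352/16 = 22) and the range 2 to 42, so the CV is an assumption. Its limits are:
- Smallest: one village at 2, one at 42, fourteen at 22. SD = √(800/16) = 7.07; CV = 7.07/22 = 0.32.
- Even spread from 2 to 42: CV 0.56.
- Largest: half at 2, half at 42. SD = 20; CV = 20/22 = 0.91.

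| CV | Design effect | 14 df power | Normal power |
|---|---|---|---|
| 0.32 | 1.210 | 76.9–78.2% | 80.5–81.7% |
| 0.56 | 1.253 | 75.7–77.0% | 79.3–80.5% |
| 0.91 | 1.356 | 72.8–74.1% | 76.5–77.8% |

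Summing m/(1 + (m − 1) × ICC) over villages, as an efficiently weighted GEE would, gives effective totals of 264.9, 257.0 and 237.1. The CV formula gives 264.3, 255.5 and 236.1, so it is not materially pessimistic. At moderate CVs the degrees of freedom account for most of the shortfall.

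**Where the claim survives on 14 df, and where it does not.**
- Equal villages, N = 320: power is exactly 80% at an ICC of 0.0079 (unpooled), 0.0064 (pooled) or 0.0058 (log-odds). At the cited smoking ICC of 0.00272 it is 81.9–83.0%.
- All 352 women retained, arms of 188 and 164, equal villages (design effect 1 + 21 × 0.01 = 1.21): 80.0–81.5%. At CV 0.56: 78.0–79.6%.
- The same arms less the planned 10% (352 × 0.9 ≈ 317), equal villages: 76.9–78.5%.

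**The case against.** Table 3 is correctly computed under its own labels, so this is a mismatch between the power method and the analysis method, not a slip in calculation. The plan promises a small-sample correction without naming it, so the t reference on 14 df is inferred. That is fair, but it is the natural reading of a sentence that gives the degrees of freedom as the reason for the correction.

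The figure of 320 is a planning floor. Of the 352 women, 222 (63%) enrolled at 24 weeks or later, so pregnancy loss may be below 10%, and women lost to follow-up stay in the primary analysis as tobacco users. Power could therefore lie near 80% on either side. This stands, and it belongs beside the corrected figure. It does not rescue a sentence tied to N = 320, and it needs near-equal villages as well.

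The CV of 0.91 is an arithmetic bound, not a likely pattern; the village-size range was known only after recruitment. That also stands, but unequal sizes can only lower power, and the current document reports them while leaving the claim unqualified.

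Finally, Table 3 already shows 76% and 71% at higher ICCs, and the power section cites a much lower ICC: "For the proportion currently smoking the estimated ICC was 0.00272". Readers are thus told that power depends on the ICC. The disputed sentence, however, names 0.01, and the same section cites 0.01 to 0.03 from another community trial.

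**Conclusion.** The concern holds. At ICC 0.01, N = 320 and one-sided 0.05, the planned test on 14 df has about 78–79% power with equal villages, not more than 80%. That is 3.5 points below the normal-based figure on each form of the test. An even spread of village sizes from 2 to 42 brings it to about 76–77%; the extreme bound is 73–74%. The 78–79% rests on reading the small-sample correction as a t reference on 14 df; the lower figures rest also on an assumed size distribution. The shortfall is small and leaves the design and the analysis method sound, but the sentence is wrong as written.

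A lesser point, on which this conclusion does not depend: the sidedness of the primary comparison appears only in the Table 3 heading. The Data Analysis Plan gives no alpha, sidedness or interval for the between-condition effect, while the mediation paths are specified as two-sided 0.05. A one-sided p between 0.025 and 0.05 could be called either way. If the primary test were two-sided 0.05, 14-df power at ICC 0.01 and N = 320 would be about 65–67% with equal villages and about 60% at the extreme CV.

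**What to change.** Recompute both columns of Table 3 with a t reference on the available df (14, or 13 if the size stratum is counted) and the actual village sizes. Replace the power sentence with the result, for example: *With an ICC of 0.01, a one-sided 0.05 test on 14 df and 320 women, power at 6 months postpartum is about 78–79% with equal village sizes and lower with the observed sizes; with equal sizes it exceeds 80% for an ICC below about 0.006, or at ICC 0.01 if all 352 women remain eligible.*

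Name the small-sample correction in the Data Analysis Plan. State there the alpha and sidedness of the primary test, with a matching interval for the between-condition effect: 90% if one-sided 0.05, 95% if two-sided 0.05. Do this before the primary analysis.

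The cost is one recomputed table and a few sentences. No participants are added and the analysis method does not change; the only downside is a slightly less favourable stated power.

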Focus Group Qualitative Analysis. Sample characteristics were summarized using descriptive statistics. Audiotapes were fully transcribed with statements in Yupik translated locally. Focus group data were analyzed using content analysis and NVivo 10 to facilitate and streamline our analysis. Codes and categories were developed around the phenomena of interest. Initially these codes were based on the themes in our moderator guide; these themes have been refined and revised to incorporate themes that emerge from the data. In addition to open coding, planned comparisons across categories of interest were carried out (e.g., tobacco use status, gender), and connections established between identified categories. The analysis process was enhanced through memo writing and summarizing of emerging themes by the facilitators after each focus group. Focus group themes were discussed and refined with the facilitators until consensus is reached, and will be reviewed with our CAC. The analysis process was documented and outlined via the use of data management software, NVivo 10. Next qualitative findings will be synthesized with our health communications framework and relevant literature.

Individual Interviews Data Analysis: Data was analyzed using frequencies and other descriptive statistics for the overall sample. Trends within and between subgroups (e.g., pregnant women who use vs. do not use tobacco) were examined using the Chi-square (exact) or two-sample rank sum test. The investigative team synthesized the findings with our health communication framework and the literature. Results and recommendations were reviewed and finalized with our CAC, Northwest Strategies and nDigiDreams.

Phase II:

Power Statement:

Sample size calculations are based on the primary endpoint of tobacco use at 6 months postpartum. From our pilot data, of the 400 women who reported tobacco use during the 3 months prior to pregnancy, 83% reported tobacco use during the prenatal period and 69% at 6 weeks postpartum. Among the 17% of women

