We will follow procedures suggested by MacKinnon to assess mediation (**Aim 2**), fitting three GEE models to the data. We will first estimate the intervention effect separately for the dependent variable (with regression adjustment for covariates). That model provides an estimate of the total effect of the intervention, which MacKinnon labels C. Next we will estimate the intervention effect for each mediator (with regression adjustment for covariates); that model provides an estimate of the effect of the intervention on the mediator, which MacKinnon labels A. Finally we will estimate the mediated intervention effect for the dependent variable by adjusting for the mediator (and covariates); that model provides an estimate of the unmediated (i.e., direct) intervention effect, which MacKinnon labels C, and the intervention-adjusted effect of the mediator on the dependent variable, which MacKinnon labels B. Assuming an ICC of 0.01 and an effective sample size of 270 subjects after correction for the ICC, there will be 80% power to detect an effect size of at least 0.35 standard deviation units for paths A and B assuming a two-sided, alpha=0.05 test at 6-months postpartum.

Treatment condition differences on changes in other variables targeted (see Table 4) will be examined using GEE with a logit (binomial outcome) or identify (continuous outcome) links as appropriate.

We will summarize the cost of the program per pregnant woman enrolled (reached) along with cost per woman abstinent from tobacco at 6 months postpartum follow-up using descriptive statistics.

Endpoints

Primary:

Biochemically confirmed tobacco abstinence at 6-months post-partum.

Secondary:

Biochemically confirmed tobacco abstinence at end of pregnancy. Also, changes in proposed theory-based mediators of intervention efficacy.

Project Timeline

We have received approval from NIH to extend out the study timeline from 5 to 6 years total. We are currently beginning the 5th year of our 6-year NIH grant. Table 4 shows the timeline for the remaining Phase II

activities. We will request from NIH a 7th project year as a no-cost extension to complete analyses and dissemination if necessary and long as remaining funds permit.

Table 4

PROJECT TIMELINE, YEARS 3-7,
Dates: May 1, 2015 – April 30, 2020

Activity	Year 3 2015-2016				Year 4 2016-2017				Year 5 2017-2018				Year 6 2018-2019				Year 7 2019-2020 No Cost Extension					

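### The >80% power for the primary endpoint at ICC 0.01 assumes a one-sided 0.05 test with a normal reference; the Aim 1 test has no stated alpha or sidedness, and on the plan's 14 df power is 78-79% one-sided and 66-67% two-sided

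*Combined protocol and SAP*

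**What the plan says.** All the relevant text is under Statistical Considerations, Phase II.

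- **Power Statement.** "Sample size calculations are based on the primary endpoint of tobacco use at 6 months postpartum". The rates are given as "we estimate the rate of tobacco use at 6 months postpartum to be 70% in our control villages and 55% in the intervention villages", and the design as "16 villages total, average village participant size of 20 (total sample size = 320" women). Table 3 is titled "Table 3. Power estimates for 1-sided alpha=0.05 test" and shows 81% for this comparison at ICC 0.01. The text concludes: "With an ICC of 0.01 we will have >80% power to detect the hypothesized differences between conditions at 6 months postpartum". That sentence does not mention sidedness.
- **Data Analysis Plan, Aim 1.** The 6-month rate is compared between conditions by GEE with a logit link. The plan notes that 14 df are available for the intervention test, commits to a small-sample correction, and adjusts for the village-size stratum. It states neither an alpha nor whether the test is one- or two-sided. The primary rate "will be summarized for each condition (point estimate and 95% CI").
- **Data Analysis Plan, Aim 2.** The mediation power for paths A and B is given "assuming a two-sided, alpha=0.05 test at 6-months postpartum".

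**The concern.** The power claim and the planned analysis do not describe the same test. The power table uses a one-sided 0.05 criterion and, as the working shows, a normal reference. The analysis section recognises that inference rests on 16 villages and needs a small-sample correction, but it leaves the decision rule for the primary comparison open. The only sidedness stated in the analysis section is two-sided, for Aim 2 at the same time point.

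Two things are at stake. First, the stated chance of detecting the hypothesised 15-point difference may be too high for the test that will be run. Second, because sidedness is not fixed in the Aim 1 text, it could be settled after results are seen.

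**Working it through.** **Inputs.** Control 70%, intervention 55%; 16 villages averaging 20 women, 320 in total; ICC 0.01 (Power Statement). Eight villages per arm (Phase II target accrual), so 160 women per arm. 14 df (Data Analysis Plan).

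**Common quantities at ICC 0.01**
- Design effect = 1 + (20 − 1) × 0.01 = 1.19.
- Effective n per arm = 160 / 1.19 = 134.5.
- Unpooled SE = √[(0.70×0.30 + 0.55×0.45) / 134.5] = √(0.4575 / 134.5) = 0.0583.
- Pooled SE, mean rate 0.625 = √[2×0.625×0.375 / 134.5] = 0.0590.
- Standardised effect = 0.15 / 0.0583 = 2.57 (unpooled), or 0.15 / 0.0590 = 2.54 (pooled).

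**Step 1: reproduce Table 3 (one-sided 0.05, normal, pooled variance under the null).**
Power = Φ[(0.15 − 1.645 × 0.0590) / 0.0583] = Φ(0.906) = 81.8%, against 81% in the plan. The unpooled version gives Φ(2.57 − 1.645) = 82.3%.

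| ICC | 55 vs 70%: recomputed / Table 3 | 65 vs 80%: recomputed / Table 3 |
|---|---|---|
| 0 | 87.3 / 87 | 91.6 / 91 |
| 0.001 | 86.7 / 86 | 91.2 / 91 |
| 0.01 | 81.8 / 81 | 87.0 / 86 |
| 0.02 | 76.5 / 76 | 82.3 / 82 |
| 0.03 | 71.7 / 71 | 77.8 / 77 |

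All ten cells agree within about 1 point. The one-sided label is therefore accurate, and the figures are those of a normal reference.

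**Step 2: change only the reference distribution (one-sided 0.05, 14 df).** The critical value rises from 1.645 to 1.761. Noncentral t power is 78.8% with noncentrality 2.57 and 77.9% with 2.54, so 78-79%.

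**Step 3: change only the sidedness (two-sided 0.05, normal).** Pooled: Φ[(0.15 − 1.96 × 0.0590) / 0.0583] = 72.2%. Unpooled: Φ(2.57 − 1.96) = 73.0%.

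**Step 4: change both (two-sided 0.05, 14 df).** The critical value is 2.145. Power is 66.7% (unpooled) or 65.7% (pooled), so 66-67%. If the stratum adjustment costs one df, 13 df gives 65-66%.

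**Step 5: other ICCs, two-sided 0.05, 55 vs 70%**

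| ICC | Normal | 14 df |
|---|---|---|
| 0 | 79-80% | 73-74% |
| 0.01 | 72-73% | 66-67% |
| 0.02 | 66-67% | 59-60% |
| 0.03 | 60-61% | 54-55% |

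**Separating the two effects (unpooled, ICC 0.01).** Sidedness alone costs 82.3 − 73.0 = 9.3 points. The 14-df reference alone costs 82.3 − 78.8 = 3.5 points. Together they cost 82.3 − 66.7 = 15.6 points.

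**The case against.** The other side has a good case on several points.

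- **The table hides nothing.** Its title gives the one-sided basis and its figures are right for that basis. This stands: there is no calculation error.
- **Aim 1 is directional.** It hypothesises lower tobacco use, and the Power Statement cites a meta-analysis favouring behavioural interventions in pregnant smokers. This gives some support to a one-sided test. But the plan does not use it to justify a one-sided 5% level, and the same section says there is no literature guidance for baseline non-users, who are eligible.
- **Aim 2 is a different question.** A two-sided level for mediation paths does not contradict a one-sided primary test. That is correct. It shows what convention the plan uses elsewhere, but it does not settle the Aim 1 rule.
- **Little can change, because recruitment is complete.** This is true of the sample size, but not of the analysis text.

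Two stronger readings are tempting, and the documents support neither. A reader might infer from the 95% CI that the primary test must be two-sided, or that some results counted as power would have an interval covering no effect. The interval is specified for each condition's rate; the plan defines no interval for the between-arm effect. A reader might also infer that the risk of a false claim of benefit is 5% instead of 2.5%. That holds only if the final GEE test is run one-sided at 0.05, which the plan does not say.

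**Conclusion.** The concern holds in a limited form. The statement of more than 80% power is correct for a one-sided 0.05 normal test at ICC 0.01 and for no stricter version considered here. It falls just short, at 78-79%, once the plan's 14 df are used, even if the test stays one-sided. If Aim 1 is tested at the two-sided 0.05 used for Aim 2, power is 72-73% with a normal reference and 66-67% on 14 df. It would be wrong to put the whole drop to 66% down to sidedness, since part of it comes from the t reference. The 66-73% range belongs to ICC 0.01 only.

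These figures use the plan's rates and 20 women in every village, with the small-sample correction represented by a t reference because the plan does not name one. Actual enrolment ran from 2 to 42 women per village, and the documents do not give the coefficient of variation. If it is assumed to lie between 0.4 and 0.8, two-sided power at ICC 0.01 would be about 71% down to 68% (normal), or 66% down to 62% (14 df).

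The trial is not invalidated. Its primary decision rule is incomplete and its headline power is optimistic for the analysis described.

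**What to change.** Before analysis:

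1. In the Aim 1 paragraph of the Data Analysis Plan, state that the primary GEE test is two-sided at 0.05, consistent with Aim 2. If a one-sided test is kept, state its level there and justify it.
2. Recompute Table 3 and the power sentence for that test, using 14 df, or 13 if the village-size adjustment costs one. Name the small-sample correction.

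The cost is a few sentences and a recalculated table. No further women are needed and the sample size stays as it is. The downside is a lower stated power at ICC 0.01: about 66-67% two-sided on 14 df, or 78-79% if a justified one-sided test is retained.

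### The between-arm comparison of recruitment rates uses a chi-square test that ignores village randomisation, unlike the GEE planned for retention; its p-value is too small if uptake clusters by village

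*Combined protocol and SAP*

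**What the plan says.** Under Phase II, Data Analysis Plan, reach is defined village by village: "To assess reach of the program in each village, we will calculate the proportion of subjects enrolled to total eligible subjects". The between-arm test follows: "We will compare the recruitment rates between control and intervention villages using the chi-square test". The only further statement is "Potential village effects on recruitment rate will be explored", which does not change the named test.

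The next paragraph treats baseline data in the same way: "Baseline demographics will be summarized and compared between intervention and control villages using the chi-square test for categorical variables", with t or rank-sum tests for continuous variables.

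Elsewhere the section respects the design. Tobacco use, retention to 6 months postpartum, and village differences in exposure and implementation are all analysed by GEE. For the intervention test the plan says "Because only 14 df are available for the test of the intervention we will employ a small sample correction to the standard GEE", and then "For these analyses, the stratification factor (village size) will be adjusted for in the analysis".

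On clustering, the Power Statement cites community ICCs of 0.002 to 0.012 for survey variables (0.00272 for current smoking). For other community trials it says "the ICC ranged from 0.01-0.03 for the four outcome variables at baseline". None of these is an ICC for recruitment. Under Actual accrual the plan reports: "Study villages were more or less interested in participating, with a range of 2 to 42 women enrolled in the 16 study villages".

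**The concern.** Women in one village share the same clinic staff, council and local interest in the study, so their decisions to enrol may be correlated. A pooled chi-square test takes its standard error from the number of women, although only 16 units were randomised. With any positive ICC it rejects too often.

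This is the plan's only between-arm test of reach. Assignment was already in effect during recruitment, and some recruitment routes differed by arm. Some women came through the Native Sister, generic postcards went to control villages, and campaign postcards went to intervention villages. Whether uptake differed by arm is therefore a fair question, and the risk is a false report that it did. The plan is also inconsistent: two binary process measures, compared between the same villages, are tested under different assumptions.

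**Working it through.** **1. The plan's own clustering arithmetic.** Table 3 uses 16 villages of 20 women and one-sided alpha 0.05. The design effect is DE = 1 + (20 − 1) × ICC. At ICC 0.01, DE = 1.19 and the effective size per arm is 160/1.19 = 134.5, or 269 in total; the plan states 135 and 270. For 55% v 70%, with mean 0.625:

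(0.15 − 1.645 × √(2 × 0.625 × 0.375/134.5)) / √((0.70 × 0.30 + 0.55 × 0.45)/134.5) = 0.91, so power is 81.8%; the plan states 81%.

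All ten cells of Table 3 reproduce within 2 points. The same design effect is used below.

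**2. Eligible women per village (assumed).** The documents give no count, so two routes are used.
- *First visits* (table under Randomization, band midpoints). That table shows 19 villages with at least 15 women, while the text says 16. The 16 smallest of them total 7 × 17 + 8 × 22.5 + 28 = 327 in 9 months; the 16 largest total 4 × 17 + 8 × 22.5 + 28 + 3 × 40 = 396. Scaling by 25/9 to the 25-month recruitment period gives about 57 and 69 per village. With each village's count rounded down, the totals are 903 and 1,095, or 56 and 68 per village.
- *Births* (over 600 a year, Community and Study Setting). 600 × 25/12 = 1,250. The 16 villages' share of all tabulated first visits is 327/655 to 396/655, giving 624 to 756, or 39 to 47 per village. Removing Bethel's population share (6,000/25,000) leaves 474 to 574, or 30 to 36 per village.

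The enrolled mean of 22 is only a limiting bound, because 22 eligible per village would mean 100% uptake.

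**3. False-positive rate.** The plan states no alpha for this test; two-sided 5% is assumed. With m eligible women per village:

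rate = 2 × P(Z > 1.96/√(1 + (m − 1) × ICC))

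Example: m = 56, ICC 0.01 gives DE = 1.55, 1.96/√1.55 = 1.574, rate 11.5%.

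| Eligible per village | ICC 0.002 | 0.00272 | 0.01 | 0.03 |
|---|---|---|---|---|
| 22 (bound) | 5.5% | 5.7% | 7.5% | 12.5% |
| 30 | 5.7% | 5.9% | 8.4% | 15.2% |
| 47 | 6.1% | 6.5% | 10.5% | 20.4% |
| 56 | 6.3% | 6.8% | 11.5% | 22.9% |
| 68 | 6.6% | 7.1% | 12.9% | 25.9% |

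Beta-binomial simulation with unequal village sizes (40,000 null trials per setting) gave 8.2% and 15.3% at a mean of 29.5 per village, and 13.6% and 27.4% at a mean of 68.4, for ICC 0.01 and 0.03. Hence 8-14% and 15-27%. A continuity correction lowers the rates by about 1 to 2 points and does not restore 5%. A stratified t-test on the 16 village proportions (13 df) stayed at about 5%.

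**4. Actual totals, 188 v 164 enrolled.** Equal eligible numbers per arm are assumed. The chi-square has no continuity correction. Adjusted p refers z/√DE to t with 14 df.

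| Eligible total | Chi-square p | Adjusted p, ICC 0.01 | Adjusted p, ICC 0.03 |
|---|---|---|---|
| 474 | 0.012 | 0.043 | 0.086 |
| 574 | 0.040 | 0.098 | 0.172 |
| 624 | 0.053 | 0.121 | 0.207 |
| 756 | 0.080 | 0.170 | 0.276 |
| 903 | 0.102 | 0.210 | 0.333 |
| 1,095 | 0.120 | 0.250 | 0.387 |

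The split between arms matters too. At an illustrative 976 eligible (61 per village), 480 intervention and 496 control gives chi-square p = 0.047; the reverse gives 0.22.

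**5. Baseline tests.** At 22 enrolled per village the formula gives 5.5% at ICC 0.002 and 8.0% at 0.012.

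**The case against.** The strongest reply is that little hangs on this test. Recruitment is not an endpoint, it was already complete, and no decision in the plan depends on the result. Village proportions will be shown and village effects explored, so readers will see much of the clustering. All of that stands and limits the weight of the point. It does not make the named test valid.

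The second reply concerns size. A reader might infer that the false-positive rate is 12-27%. The documents do not support that as the single answer. It takes the largest of the assumed denominators and leaves out the lower ICCs that the Power Statement also cites. First visits are not eligible women: minors, women at 37 weeks or more, and women without a telephone are excluded. The reach sentence follows one that lists women screened, excluded and eligible, so the denominator may well be screened-eligible women, which is a smaller count. This objection is accepted, and the range is given in full.

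A reader might also infer from the spread of 2 to 42 enrolled that the recruitment ICC is well above 0.03. Those are counts without denominators, from villages of different sizes. They make clustering plausible but do not establish an ICC.

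**Conclusion.** The inconsistency is certain from the text: recruitment is tested as if women had been randomised, retention as if villages had been. For any positive recruitment ICC the chi-square test is anti-conservative.

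The size is conditional. Assuming 30 to 68 eligible women per village and a two-sided 5% test, the false-positive rate is about 6-7% at ICC 0.002-0.003, 8-14% at 0.01 and 15-27% at 0.03. The ICCs are borrowed from other variables.

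A reader might conclude that the reported finding would be reversed, or that the trial's main result is in doubt. Neither follows. With equal arms and 903 to 1,095 eligible, both tests are non-significant. At 474 and ICC 0.01 both are significant. At 574 they disagree at both ICC 0.01 and 0.03. The outcome turns on eligible counts that the documents do not give. The primary analysis uses GEE with a small-sample correction and is unaffected. The point is worth correcting because it concerns the only between-arm test of reach and costs almost nothing. The baseline tests are a minor matter.

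**What to change.** In the Phase II Data Analysis Plan, replace the chi-square test for recruitment with one of two methods:
- GEE with the small-sample correction and village-size adjustment that the plan already specifies, applied to enrolled v eligible; or
- a test on the 16 village enrolled-to-eligible proportions, stratified by village size.

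In the same sentence, confirm which count is the eligible denominator: screened-eligible women, or the positive pregnancy tests per village described under Program Evaluation. The p-value is sensitive to that choice.

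As a minor companion change, report baseline characteristics descriptively or with cluster-adjusted tests.

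The cost is one or two sentences. No new data are needed, because the plan already calls for the enrolled-to-eligible proportion in every village.
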